### **3.2.3        Subject Restrictions During the Study**

#### **3.2.3.1      General and Dietary**

To avoid false positive drugs of abuse screening results, no food or drink containing poppy seeds (eg, specialty breads and muffins) will be allowed for 72 hours before the screening visit.

### **3.2.3.2      Contraception and Pregnancy Avoidance Procedures**

Female subjects must be post-menopausal (defined as amenorrhea for 12 consecutive months without an alternative medical cause or documented serum follicle-stimulating hormone level in the post-menopausal range) or surgically sterile (ie, hysterectomy, bilateral tubal ligation, or bilateral oophorectomy). NOTE: procedures and laboratory test results must be confirmed in the medical record, by physical examination, or by official written confirmation of a procedure; or, if of childbearing potential, practicing a medically approved and highly effective method of contraception (defined as those which result in a low failure rate [ie, less than 1% per year] when used consistently and correctly).

All female subjects of childbearing potential must have a negative pregnancy test at Screening and before dosing with study drug. Women of childbearing potential must agree to be heterosexually inactive from at least 21 days prior to enrollment and through 3 months after the final vaccination or agree to consistently use any of the following methods of contraception from at least 21 days prior to enrollment and through 3 months after the final vaccination: condoms (male or female) with spermicide, diaphragm with spermicide, cervical cap with spermicide, intrauterine device, oral or patch contraceptives, Norplant®, Depo-Provera®, or other FDA-approved contraceptive method which is designed to protect against pregnancy. Periodic abstinence (eg, calendar, ovulation, symptothermal, post-ovulation methods) and withdrawal are not acceptable methods of contraception.

Male subjects must agree to consistently use appropriate contraception and to refrain from sperm donation through 3 months after the final vaccination.

Subjects will be provided with information on acceptable methods of contraception as part of the subject informed consent process and will be asked to sign a consent form stating that they understand the requirements for avoidance of pregnancy.

## **3.3      Withdrawal of Subjects From the Study**

### **3.3.1      Reasons for Withdrawal**

Subjects can withdraw consent and discontinue from the study at any time, for any reason, without prejudice to further treatment.

The investigator can also withdraw a subject upon the request of Moderna Therapeutics, Inc. or if Moderna Therapeutics, Inc. terminates the study. Upon occurrence of a serious or intolerable AE, the investigator will confer with the Sponsor or designee. If a subject is discontinued because of an AE, the event will be followed until it is resolved or until stable. In the event of a safety concern that results in withdrawal from further vaccination, the subject will be continued in the trial for safety evaluations.

Every reasonable attempt will be made to follow withdrawn subjects for safety. The reason for subject withdrawal will be documented.

The investigator, in consultation with the Sponsor's medical monitor, **may** withdraw a subject from further vaccination if the subject experiences any of the following:

1. Becomes pregnant;
2. Develops, during the course of the study, symptoms or conditions listed in the exclusion criteria;
3. Experiences an AE (other than reactogenicity) after vaccination that is considered by the investigator to be related to treatment and is of Grade 3 (severe) or higher severity;
4. Experiences an AE or SAE that, in the judgment of the investigator, requires study drug withdrawal due to its nature, severity, or required treatment, regardless of the causal relationship to treatment;
5. Experiences a clinically significant change in clinical laboratory test results, vital signs, or general condition that, in the judgment of the investigator, requires treatment withdrawal;
6. Experiences anaphylaxis clearly attributed to study vaccine; or
7. Experiences generalized urticaria related to the study vaccine.

The reason for withdrawing from further vaccination will be recorded. In addition, if a subject refused further vaccination they will be continued in the trial with all planned visits and assessments. The recording of the reason for vaccination refusal will be documented.

### **3.3.2 Handling of Withdrawals**

When a subject withdraws from the study, the reason(s) for withdrawal will be recorded by the investigator on the relevant page of the electronic case report form (eCRF). These subjects will also be requested to complete all Visit 7 assessments. Any subject who fails to return for final assessments will be contacted by the site with a minimum of 3 telephone call attempts, followed by a certified letter.

Lost to follow-up is defined by the inability to reach the subject after a minimum of 3 documented telephone calls, faxes, text messages, or emails as well as lack of response by subject to 1 registered mail letter. All attempts should be documented in the subject's medical records.

### **3.3.3 Replacements**

If a subject is withdrawn, who is significantly outside the allowed vaccination window, or is lost to follow-up from the study, the decision on whether or not to replace the subject will be made by the Sponsor in conjunction with the principal investigator.

## **3.4 Study Treatments**

### **3.4.1 Method of Assigning Subjects to Treatment Groups**

Subjects will be randomly assigned in a sequential manner to a dose level cohort after all entry criteria have been satisfied on Visit 1. A randomization table will be pre-generated, and only the unblinded pharmacy personnel will have controlled access. Within each dose level cohort, 20 subjects will be randomly assigned to receive either VAL-181388 (25, 50, or 100  $\mu$ g) or placebo in an overall ratio of 3:1. The first 4 subjects within each dose level cohort will be randomly assigned to receive VAL-181388 (25, 50, or 100  $\mu$ g) or placebo in a 3:1 ratio. Only after review by the IST of the blinded safety data (reactogenicity, safety laboratory results, and AEs) through 7 days following the first vaccination of the sentinel safety lead-in for each cohort planned, will approval be given to allow randomization of the remainder of that cohort. The remaining 16 subjects within each dose level cohort will be randomly assigned to receive either VAL-181388 (25, 50, or 100  $\mu$ g) or placebo in a 3:1 ratio.

### **3.4.2        Treatments Administered**

Up to 60 subjects will receive 1 of the following treatments based on the treatment to which they are randomly assigned. Dose level cohorts will advance in a sequential manner after review of all safety data through 7 days after the final vaccination of the previous dose level cohort by the SMC (inclusive of reactogenicity, safety laboratory test results, and AEs). All vaccines will be administered as a 2-injection schedule (28 days apart), into the deltoid muscle (IM), preferably in the non-dominant arm:

- Cohort 1 (N = 20): 25 µg VAL-181388 or placebo (ratio = 3:1)
- Cohort 2 (N = 20): 50 µg VAL-181388 or placebo (ratio = 3:1)
- Cohort 3 (N = 20): 100 µg VAL-181388 or placebo (ratio = 3:1)

The clinic will be appropriately staffed, trained on emergency resuscitation, and have stocked available rescue medications (such as epinephrine, steroids, antihistamines, and IV fluids) should any severe reaction (eg, anaphylactoid or profound urticaria) occur which requires immediate intervention.

#### **3.4.2.1      Dose Escalation**

##### **Internal Safety Team**

An IST will oversee the safety of the trial and will review blinded safety data during Part A of the study to ensure adherence to the protocol, monitor safety laboratory test results and reactogenicity, and raise concerns to the SMC should there be safety issues or operational challenges that could affect subject safety. Pause rules have been pre-established to trigger ad-hoc SMC reviews, if required (Section 3.4.2.2), and the IST will review (blinded review) safety laboratory test results, vital sign measurements, reactogenicity, and any AEs (all with toxicity grading) during the active vaccination phase of the trial. In addition, recruitment rates, timing of vaccination sequence, and window adherence will be reported to the IST. The chairperson of the IST may request that additional data be provided to the SMC that relates to the safety of subjects (eg, study conduct, quality issues, or safety concerns).

The 4 subjects in the sentinel safety group will receive VAL-181388 or placebo at Visit 1. The IST will review blinded safety data through at least 7 days after vaccination, inclusive of

reactogenicity, laboratory results, and any AEs from all subjects in the sentinel safety group. The IST is responsible for opening randomization to the remainder of the dose level cohort for that dose level after review of the safety data.

At minimum, the IST will be composed of the Sponsor's study medical monitor lead, the contract research organization's medical monitor, and the principal investigator. The pharmacovigilance officer will oversee safety aspects of the study and will participate as needed. Additional ad hoc members may be included as needed.

### **Safety Monitoring Committee**

Dose escalation will proceed following review of blinded safety data by the SMC of the entire dose level cohort through 7 days following the second vaccination. In addition, the SMC will review prior dose level cohort reactogenicity and accumulated AEs at the time of the scheduled safety review to allow the SMC an aggregate view of overall safety. The SMC safety data assessment will include the following blinded summary data: 1) toxicity scoring of safety laboratory test results through 7 days following the second vaccination (through Visit 5); 2) toxicity scoring of vital signs and reactogenicity through 7 days following the first and second vaccination (through Visit 5); 3) all unsolicited AEs (with grading and attribution). Data will be prepared by dose cohort and timing relative to each vaccination. As safety data on all cohorts accumulate, the SMC also review ongoing AEs as well as cumulative safety laboratory test results, reactogenicity, and AEs across vaccine doses for subjects remaining in Part A of the study, thereby providing a cumulative and comprehensive review of safety. Should a cohort pause occur due to pre-specified criteria, the SMC will be convened for an unscheduled (ad hoc) meeting and be provided with specific safety data related to the trigger of the pause. If no pause rules (Section 3.4.2.2) are triggered or any other safety concerns are identified, the SMC may recommend escalation to the next dose level.

In addition, the Sponsor will submit available safety data for the 25 and 50 µg dose cohorts and recommendations of the SMC to the Center for Biologics Evaluation and Research (CBER) prior to initiation of the 100 µg cohort.

The SMC may recommend advancement to the next dose level, request additional information prior to providing a recommendation, recommend stopping the study, recommend changes to study conduct and/or the protocol, or recommend additional operational considerations due to safety issues that arise during study conduct. The Sponsor has the authority to accept (or

amend) the SMC recommendations, to stop the study at any time, to request a cohort pause for safety concerns (to be addressed by the SMC), and to request additional consultation during study conduct for either safety concerns or operational issues. The SMC will also be convened should a pause rule (Section 3.4.2.2) be triggered or at the request of the IST, the investigator, or the Sponsor.

The SMC will be comprised of 3 voting and independent members who are medical doctors familiar with Phase 1 clinical trial and safety review and independent from the trial. In addition, a biostatistician not associated with the trial will prepare the safety data (non-voting member), and a coordinator not associated with the trial will organize and record decisions of the SMC (non-voting member). The SMC may decide to include a non-medical person to weigh in on ethical issues if the need arises.

### **3.4.2.2 Pause Rules**

During the active vaccination period, if any of the following events occur and are assessed to be potentially VAL-181388 related, the study will be paused for further enrollment and vaccination and an unscheduled SMC will be convened to assess specific data concerns and make recommendations:

- Two or more severe reactogenicity events of the same nature (whether systemic or local) within a dose cohort following any single (eg, the first, the second) vaccination
- Two or more Grade 3 (or greater) laboratory toxicities within a cohort and of the same nature
- One or more SAEs assessed as vaccine related, including any systemic hypersensitivity reaction

An unscheduled SMC may also be convened (with vaccination pausing if deemed necessary), by the investigator, IST, or Sponsor, if any other significant safety or tolerability issues are identified in the comprehensive review of available data that warrant further evaluation before additional subjects are dosed. This may include emerging nonclinical data, clinically relevant AEs, or relevant data from other sources indicating safety concerns even if the event(s) per se does not meet the criteria specified in this section.

Should a pause be triggered in the study, then each subject's visits will continue until the next scheduled vaccination visit. Should a pause affect a subject's vaccination visit, then the window for that subject's vaccination visit will be suspended until the pause is lifted and vaccination can resume. Once the pause is lifted at the site, vaccination should be reinstated as soon as possible. Visits should thereafter be scheduled as if they had received their second vaccination within the 28 (+7) day time window.

Should a pause be prolonged such that the vaccination sequence cannot establish a 28 (+ 7) day time window, the Sponsor has the option to add additional subjects in a dosing cohort to achieve the original number of subjects planned to be dosed within the 28 (+7) day time window. If a subject is in the screening period during this pause and more than 28 days has transpired, they may be rescreened for study eligibility as long as they continue to provide consent to participate in the study.

The objectives of the study are to characterize safety, tolerability, and immunogenicity of multiple ascending doses of VAL-181388. Thus, this protocol is written with some flexibility to reflect the dose-finding nature of this Phase 1 clinical study. Modifications to the dose level may be required to achieve the scientific goals of the study and/or to ensure appropriate safety monitoring of the study subjects. Identity of Investigational Product

VAL-181388 is composed of 1.6 mg/mL of CX-000314, the VAL-181388 mRNA drug substance, formulated in a mixture of 4 lipids, including MC3 (DLin-MC3-DMA, a novel ionizable lipid), cholesterol, DSPC (1,2-Distearoyl-sn-glycero-3-phosphocholine), and PEG2000-DMG (1,2-Dimyristoyl-sn-glycerol, methoxypolyethyleneglycol), to form an mRNA-lipid complex (LNP) in 7.0% propylene glycol, 1 mM DTPA (diethylenetriaminepentaacetic acid), 100 mM Tris buffer.

The placebo is 0.9% Sodium Chloride Injection, USP or BP.

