### 1.3 Clinical Studies

No clinical studies have been conducted with VAL-181388. No reproductive or developmental toxicity studies have been completed to date with VAL-181388. Women of childbearing potential are included in this Phase 1 clinical study. They must agree to be heterosexually inactive from at least 21 days prior to enrollment and through 3 months after the final vaccination or agree to consistently use protocol-specified approved methods of contraception from at least 21 days prior to enrollment and through 3 months after the final vaccination.

VAL-181388 has not yet been administered to humans. Thus, information on possible risks and adverse reactions associated with IM administration of VAL-181388 is derived from:

- Animal studies with VAL-181388, LNP components, or the similar mRNA-based influenza vaccine, VAL-506440
- Published clinical data on other mRNA-based investigational medicinal products and products encapsulated in LNPs of similar composition as the LNP formulation of VAL-181388
- The Sponsor's recent experience with mRNA-based influenza vaccines, VAL-506440 and VAL-339851, using the same LNP matrix as VAL-181388

Subjects receiving VAL-181388 are likely to experience mild-to-moderate injection site reactions as observed in studies in animals and generally observed and expected for other IM-administered vaccines. These local reactions may consist of pain, swelling, and erythema, which are transient and can be dose dependent. Possible mild to moderate systemic reactions, which are also transient, include fever, fatigue, chills, headache, myalgias, and arthralgias. In addition, other adverse events (AEs) that have been generally associated with approved IM-administered vaccines have included mild hematological and clinical chemistry abnormalities, which are usually reversible.

Subjects receiving VAL-181388 could experience signs and symptoms compatible with a CARPA response, which has been observed in the administration of approved liposomal products, contrast agents, pegylated proteins, and antibodies (Szebeni 2014), as well as for small interfering RNA products formulated in LNPs (Coelho et al 2013; Fitzgerald et al 2014). The signs and symptoms of CARPA resemble those of an acute hypersensitivity reaction. These signs can also be seen preclinically in toxicology species. However, complement activation is

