### **3.5.7.1.3 Adverse Events of Special Interest**

Certain AESIs are evaluated after the administration of immunostimulatory agents. All subjects enrolled in the study will be monitored for AESIs from enrollment through the EOS visit. The occurrence of any of these AEs will be treated as an SAE, meeting the criterion of a “medically important event.”

The list of AESIs is presented in [Appendix 2](#).

A diagnosis of an AESI will be reported to the Sponsor in an expedited manner similar to an SAE. The AESI diagnosis, as well as any medications taken to treat the condition, will be recorded in the subject’s eCRF.

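### The mandatory pause rules have no trigger for related, non-serious, non-laboratory Grade 3 or higher clinical AEs outside the solicited reactogenicity list and window

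*Protocol*

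**What the plan says.** Protocol Section 3.4.2.2 pauses enrollment and vaccination, and convenes an unscheduled Safety Monitoring Committee (SMC), if one of three events occurs during the active vaccination period and is judged potentially related:

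- "Two or more severe reactogenicity events of the same nature (whether systemic or local) within a dose cohort following any single" vaccination;
- two or more laboratory toxicities of Grade 3 or higher, of the same nature, in a cohort;
- "One or more SAEs assessed as vaccine related, including any systemic hypersensitivity reaction".

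For anything else, the next paragraph of that section says: "An unscheduled SMC may also be convened (with vaccination pausing if deemed necessary), by the investigator, IST, or Sponsor". It mentions clinically relevant AEs that miss the listed criteria, but sets no count or grade.

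Section 3.5.6 limits reactogenicity to the listed solicited signs and symptoms on the dosing day and the following 7 days. Section 3.5.7.1.3 says of AESIs: "The occurrence of any of these AEs will be treated as an SAE". Section 3.3.1, item 3, allows one subject to be withdrawn from further vaccination for an AE other than reactogenicity that is "considered by the investigator to be related to treatment and is of Grade 3 (severe) or higher severity". The SAP contains no pause rule.

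**The concern.** A study-level pause should not depend on whether a severe related symptom was anticipated on the diary card. As written, the rule is laxer for the unanticipated clinical event than for the anticipated one.

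Chills shows the problem. Section 1.3 says: "Possible mild to moderate systemic reactions, which are also transient, include fever, fatigue, chills, headache, myalgias, and arthralgias". Chills is nevertheless neither solicited in Section 3.5.6 nor graded in Table 6-3. If related chills proved severe but not serious, no number of cases would force a pause.

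What is at stake is dosing within a first-in-human cohort. The SMC's escalation review takes place once all subjects in the cohort have completed the visit 7 days after their second vaccination (Figure 3-1, note 3). It protects the next cohort, but by then the current cohort's planned doses have been given. Between the sentinel review and that point, the independent SMC meets about these events only if the internal safety team (IST), the investigator or the Sponsor asks.

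**Working it through.** **Coverage.** The documents state no operating characteristic for the pause rules, so there is no figure to reproduce. The first check is to set related event classes beside the three triggers.

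| Related event | Mandatory trigger? | Source (Protocol) |
|---|---|---|
| Severe solicited symptom, dosing day plus 7 days, two of the same nature after the same-numbered vaccination | Yes, bullet 1 | 3.4.2.2, 3.5.6 |
| Grade 3+ laboratory value, two of the same nature | Yes, bullet 2 | 3.4.2.2 |
| SAE, AESI, systemic hypersensitivity reaction | Yes, bullet 3, at one event | 3.4.2.2, 3.5.7.1.3 |
| Non-serious Grade 3+ clinical AE, off the list | No, at any count | – |
| Listed symptom starting after the window, non-serious, Grade 3+ | No, at any count | 3.5.6 |

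The last two rows are the gap. They can include some Grade 4 events: Section 3.5.7.4 grades an emergency room visit as Grade 4, but Section 3.5.7.1.2 does not make such a visit serious in itself.

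**Grade definitions.** Under Section 3.5.7.4, Grade 3 means that the event both prevents daily activity and needs medical intervention. In Table 6-3, fatigue and myalgia reach Grade 3 by preventing daily activity, and headache by that or by narcotic use. Arthralgia needs prevented activity and medical intervention, and the nausea/vomiting entry adds outpatient IV hydration. The uncovered class is therefore graded at least as strictly as headache.

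**How often an added rule would fire.** Inputs: 15 vaccine recipients per cohort (Section 3.1) and a rule of two or more subjects with the same kind of event. The true rate p per vaccination is an assumption, because the documents give none.

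P = 1 − (1−p)^15 − 15p(1−p)^14, and for either of two vaccinations, taken as independent, 1 − (1−P)².

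At p = 10%: 1 − 0.2059 − 0.3432 = 0.4510, and 1 − 0.5490² = 0.699.

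| p | One vaccination | Either vaccination |
|---|---|---|
| 1% | 1.0% | 1.9% |
| 2% | 3.5% | 6.9% |
| 5% | 17.1% | 31.3% |
| 10% | 45.1% | 69.9% |
| 20% | 83.3% | 97.2% |

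The present mandatory rules give 0% for this class at every rate. That follows from how the class is defined, so it describes the gap and is not a separate finding.

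**False pauses.** Relatedness is judged blind, so all 20 subjects in a cohort can contribute. With an assumed background rate p judged related, per vaccination and event type:

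P = 1 − (1−p)^20 − 20p(1−p)^19. Three cohorts and two vaccinations give 1 − (1−P)^6. Three independent event types give 1 − (1−P)^18.

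At p = 1%: 1 − 0.8179 − 0.1652 = 0.0169, then 1 − 0.9831^6 = 0.097.

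| p | Per cohort and vaccination | Whole study, one type | Whole study, three types |
|---|---|---|---|
| 0.1% | 0.02% | 0.1% | 0.3% |
| 0.5% | 0.4% | 2.7% | 7.8% |
| 1% | 1.7% | 9.7% | 26% |

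**Why keep the same-numbered vaccination.** Counting across both doses makes the per-subject rate 1 − (1−p)². At p = 1% the false-pause chance rises from 3.3% to 5.9% per cohort, and from 9.7% to 16.8% over three cohorts.

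**The case against.** The strongest reply is that this class was left to judgement deliberately and is well watched. Section 3.4.2.1 says that "the IST will review (blinded review) safety laboratory test results, vital sign measurements, reactogenicity, and any AEs", all with toxicity grading. There is one site, the principal investigator sits on the IST, and data entry is due within 3 business days (Section 3.7). The SMC sees all graded and attributed unsolicited AEs before escalation, and CBER receives available data before the 100 µg cohort. The discretionary paragraph names clinically relevant AEs. The residual class is also narrow: the investigator or Sponsor may call an important medical event serious, and the most common events on the same platform (Section 1.3) were local reactions, headache and malaise.

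All of that stands, and it rules out the stronger reading that severe unsolicited events go unseen or cannot stop dosing. A reader might also infer from Section 3.3.1 that a mandatory study-level rule was intended. It was not, because that item also says that the investigator may act. Nor do severe headaches force a pause whenever they occur; one starting on day 10 is outside bullet 1.

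What the reply does not supply is a threshold. Section 3.4.2.1 says: "The SMC will also be convened should a pause rule (Section 3.4.2.2) be triggered or at the request of the IST, the investigator"; a Sponsor request also counts. The IST's minimum membership is the Sponsor's medical monitor lead, the contract research organization's medical monitor and the principal investigator, whereas the voting SMC members are independent of the trial. For this class alone, calling the independent body has no pre-specified count or grade.

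Two cautions about any fix also stand. It should not count prevented activity alone as Grade 3: that would be looser than Table 6-3 is for arthralgia, would depart from the eCRF grade, and would add false pauses. The false-pause risk also grows with the number of event types, and unsolicited terms are open-ended.

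**Conclusion.** The concern holds as a modest gap in the pause rules. Related, non-serious, non-laboratory Grade 3 or higher clinical AEs outside solicited reactogenicity have no mandatory trigger at any count, and no other section or the SAP provides one. The documents do not support calling this a failure of oversight, since the IST and SMC reviews and the discretionary route all reach these events.

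The probabilities rest on assumed rates, on independence between subjects, vaccinations and event types, and on full cohorts. The coverage conclusion needs none of these. The Section 3.5.7.4 grade requires medical intervention, which should keep background rates toward the low end of the range shown. Adding the trigger is a cheap improvement that should be made.

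**What to change.** Add one bullet to Section 3.4.2.2 under the existing relatedness lead-in:

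*Two or more subjects in one dose cohort with an unsolicited clinical AE of Grade 3 or greater (graded per Section 3.5.7.4), of the same nature and after the same-numbered vaccination, not counting an isolated vital-sign value recorded under Section 3.5.9.*

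Leave the other three bullets and the discretionary paragraph unchanged. Using the Section 3.5.7.4 grade keeps the rule aligned with the eCRF. Using same nature, with no requirement for an identical preferred term, matches the existing bullets and avoids splitting similar symptoms across terms. The vital-sign exclusion is needed because Section 3.5.9 puts isolated Grade 3 or higher readings on the AE page; those stay with IST review. The bullet would run over the 28-day unsolicited period, longer than bullet 1, so that it also catches listed symptoms with late onset.

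The cost is one bullet in an amendment plus the false-pause risk tabulated above. A pause halts enrollment and vaccination study-wide, suspends second-dose windows and, if prolonged, may lead the Sponsor to add subjects. Requiring relatedness, two subjects, the same nature and the same-numbered vaccination limits that risk.
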